## 5. A Priori Statistical Methods

### 5.1. General Considerations

All tests of treatment effects of biological efficacy or clinical efficacy will be conducted at a 1-sided  $\alpha=.10$ , unless otherwise stated. Safety assessments will be conducted at a 2-sided  $\alpha=.05$ .

A repeated measures analysis refers to a restricted maximum likelihood (REML)-based, mixed effects repeated measures analysis using all the longitudinal observations at each post-baseline visit.

All analyses will follow the intent-to-treat (ITT) principle unless otherwise specified. An ITT analysis is an analysis of data by the groups to which subjects are assigned by random allocation, even if the subject does not take the assigned treatment, does not receive the correct treatment, or otherwise does not follow the protocol.

When change from baseline is assessed, subjects will be included in the analysis only if both a baseline and a postbaseline measure are available. Unless otherwise defined, Visit 3 is the baseline visit, and baseline value is defined as last value available before or at Visit 3.

All total and subscale scores will be derived from individual items. If any individual item is missing, the corresponding total and subscale scores will be considered missing, except for the ADAS-Cog13 and ADCS-iADL, which will be imputed.

A repeated measures analysis model will include the fixed, categorical effects of treatment, visit, and treatment-by-visit interaction, as well as the continuous, fixed covariates of baseline, baseline-by-visit interaction, and age at baseline.

When an analysis of covariance (ANCOVA) model is used to analyze a continuous efficacy variable, the model will contain the main effects of treatment with baseline value and age at baseline added as covariates. For ANCOVA analysis on change from baseline to Week 52 endpoint, change from baseline to last observation during treatment period will be used if patients do not have Week 52 observation available.

Categorical comparisons between treatment groups will be performed using Fisher's exact tests or logistic regression where appropriate.

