## 5.8. Subject Characteristics

Standard baseline characteristics of gender, age, and race will be summarized for all patients. Treatment group comparisons will be made using Fisher's exact test for categorical data and an ANOVA with an independent factor for treatment for continuous data. Diagnosis, illness characteristics, and baseline efficacy and safety measures will be analyzed in a similar manner.

Baseline characteristics will be summarized for the efficacy and per-protocol populations by treatment group and overall. Summaries will include descriptive statistics for continuous and categorical measures. Fisher's exact test or Pearson's chi-square test will be used for treatment-group comparisons of categorical data. For continuous data, analysis of variance (ANOVA),

with independent factors for treatment, will be used. Subject characteristics to be presented include:

- Baseline AV-45 SUVr
- Baseline Tau PET SUVr
- age
- age group: 55-64, 65-74, ≥75
- gender
- race
- ethnicity
- height
- body weight
- body mass index (weight (kg) / [height (m)])
- region
- tobacco use
- alcohol use
- years of education
- work status
- ApoE4 carrier status (carrier [ε2/ε4, ε3/ε4, ε4/ε4], noncarrier [ε3/ε3, ε2/ε2, ε3/ε2])
- ApoE4 genotype (ε2/ε4, ε3/ε4, ε4/ε4, no ε4)
- having 1 or more first degree relatives with AD
- AChEI and/or memantine use at baseline
- Baseline severity of impairment as measured by ADAS-Cog13, ADCS-iADL instrumental (ADCS-iADL) and , MMSE, MoCA, NPI, ECog, BASQID , and FAQ.

Baseline characteristics will also be listed.

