### **5.13.5. Vital Signs and Other Physical Findings**

Vital sign measurements and weight will be analyzed using continuous data (change from baseline) and categorical data (proportion of potentially clinically significant changes).

If there are multiple records of vital sign or weight measurements at baseline or postbaseline visit, the last record will be used. Summary statistics will be presented for observed values at baseline and for change from baseline results at each scheduled postbaseline visit. Systolic and diastolic blood pressure and pulse (collected in sitting position), orthostatic diastolic and orthostatic systolic blood pressures and orthostatic pulse (measurement after 5 minutes in the supine position minus that after 3 minutes in the standing position), temperature, and weight by treatment group for all subjects in the safety population will be summarized.

With the large number of the scheduled vital sign visits, the MMRM model is not suitable for the change from baseline comparison of treatments due to computational challenge. Change from baseline to each post-baseline visit at which vital signs are taken will be assessed using an ANCOVA model with treatment and as independent factors and baseline value and age as covariates in the model. This analysis will be done separately for each vital sign parameter and weight.

The incidence of treatment-emergent abnormal high or low vital signs and weight will be presented by treatment group and visit. Treatment-emergent vital sign evaluations are defined for evaluations collected after the initiation of study medication. Abnormal criteria for

postbaseline vital signs and weight are presented in [Appendix 3](#). Any vital sign or weight meeting the criteria will be considered abnormal. Treatment differences in the proportion of subjects with treatment-emergent abnormal high or low vital signs and weight will be assessed between treatment groups using Fisher's exact test at (1) any time (2) post-baseline visit.

For each vital sign at each post-baseline visit, only subjects who had a baseline result and had a nonmissing result at that post-baseline visit will be included in the denominator when computing the proportion of subjects with treatment-emergent high, low, or abnormal values.

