Summary and analyses of change from baseline in weight will be provided. The proportion of subjects with a weight gain or loss of greater than or equal to 7 percent of baseline body weight will be compared between treatment groups using Fisher's exact test at each visit and at any time. For those subjects exhibiting a weight loss of greater than or equal to 7 percent of baseline body weight, body mass index (BMI) will be tabulated by treatment and compared using an ANOVA model with factors for treatment. In addition, categories of BMI (underweight =  $<18.5$ , normal =  $\geq 18.5 - <25$ , overweight =  $\geq 25$  to  $<30$ , obese =  $\geq 30$ ) will be compared across treatment groups using Pearson's chi-square test at each visit and at any time.

A listing of treatment-emergent abnormal vital signs and weight will also be presented by subject and visit.

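### The BMI ANOVA in SAP 5.13.5 is confined to patients who lost at least 7% of body weight, so if the drug affects weight its p-value cannot be read as a drug effect on BMI

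*SAP*

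**What the plan says.** SAP 5.13.5 (Vital Signs and Other Physical Findings) plans four looks at weight or BMI.

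- **Weight change.** ANCOVA at each post-baseline visit with baseline value and age as covariates: "This analysis will be done separately for each vital sign parameter and weight".
- **Weight change of 7% or more.** "The proportion of subjects with a weight gain or loss of greater than or equal to 7 percent of baseline body weight" is compared between groups by Fisher's exact test, at each visit and at any time.
- **BMI in patients with a loss of 7% or more.** The group is set by the opening clause, "For those subjects exhibiting a weight loss of greater than or equal to 7 percent of baseline body weight". Within that group the SAP gives the analysis as follows: "body mass index (BMI) will be tabulated by treatment and compared using an ANOVA model with factors for treatment". The model has no baseline BMI and no age. The SAP does not say which BMI is meant (baseline, at the loss, or last), and it does not label the comparison descriptive.
- **BMI categories.** Underweight (below 18.5) to obese; these "will be compared across treatment groups using Pearson's chi-square test at each visit and at any time". The sentence follows the restricted ANOVA and does not state its own population.

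SAP 5.8 defines BMI as weight over height squared, and the protocol's Schedule of Activities measures height only at Visit 1. Change in BMI within a patient is therefore change in weight, rescaled. Under SAP 5.1 and 5.5, safety tests are two-sided at 0.05 with no multiplicity adjustment.

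**The concern.** Membership of the analysed group is decided after randomisation by a variable that treatment may change. Two things can then go wrong.

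First, the 7% threshold forces everyone in the subset to have lost a similar fraction of weight. An effect that shows up mainly as more patients crossing the threshold largely disappears from the comparison.

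Second, if the drug brings in a different kind of patient (heavier or lighter) from those who lose weight on placebo, the arms within the subset differ in baseline BMI. The ANOVA has no covariate to correct for that.

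The safety question behind the table is whether weight loss on drug takes patients to a low BMI. A p-value from this subset could look reassuring, or alarming, because of who was selected.

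**Working it through.** The SAP gives no figure for this analysis, so there is none to reproduce. The arm sizes come from Protocol 5.1: about 167 placebo, 45 on 3 mg and 167 on 12 mg (167 + 45 + 167 = 379, against the planned 380).

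**Assumed inputs, not in the documents.** Baseline BMI has mean 26 and SD 4.5. Weight change on placebo has mean -1% and SD 4.5%. The drug adds a mean loss of about 1, 2 or 3 percentage points in one of three patterns: the same for everyone, more in heavier patients, or more in lighter patients. Post-baseline BMI = baseline BMI × (1 + change/100). A patient enters the subset if change ≤ -7%. Each setting had 4,000 simulated trials with a one-way ANOVA across three arms. The same ANOVA in all patients is only a benchmark; the SAP does not plan it.

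**Step 1: no drug effect on weight.** The chance of entering is Φ((-7 + 1)/4.5) = Φ(-1.33) = 0.091. That gives 0.091 × 167 ≈ 15 on placebo, 0.091 × 45 ≈ 4 on 3 mg and 15 on 12 mg. The restricted ANOVA rejects in 0.051 of trials, so it holds its level.

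**Step 2: the same 2-point extra loss for everyone.** In all patients the BMI difference is 26 × (-0.02) = -0.52. In the subset, mean change is μ - 4.5 × φ(a)/Φ(a), with a = (-7 - μ)/4.5:

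- placebo, μ = -1, a = -1.33: about -9.1%
- drug, μ = -3, a = -0.89: about -9.5%

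The difference is about -0.4 points, or 26 × (-0.004) ≈ -0.1 BMI units; the simulation gave -0.12. Meanwhile the 12 mg patients entering rise to Φ(-0.89) × 167 = 0.187 × 167 ≈ 31. The effect has moved into the count, and the ANOVA does not test the count.

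**Step 3: all patterns.** Difference in mean post-baseline BMI, 12 mg minus placebo, at extra losses of about 1 / 2 / 3 points:

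| Who loses more on drug | All patients | Subset with loss ≥ 7% | Rejection rate, subset |
|---|---|---|---|
| Everyone equally | -0.26 / -0.52 / -0.77 | -0.06 / -0.12 / -0.15 | 0.049 / 0.051 / 0.051 |
| Heavier patients | -0.32 / -0.63 / -0.96 | +1.15 / +1.87 / +2.04 | 0.106 / 0.265 / 0.381 |
| Lighter patients | -0.24 / -0.50 / -0.73 | -1.22 / -2.15 / -2.66 | 0.124 / 0.318 / 0.532 |

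The three rows show the effect hidden, reversed and exaggerated. Placebo stays near 15 patients throughout, 3 mg has 6 to 13, and 12 mg has 22 to 49.

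**Step 4: a milder illustration, also assumed.** Baseline BMI 26 (SD 4); background risk of a 7% loss with logit -3.2 - 0.12 × (BMI - 26); the drug adds an independent 5% risk. Patients with a 7% loss are then 4.3% on placebo (mean baseline BMI 24.18) and 9.1% on drug (25.18), a gap of 1.0 unit from selection alone. If each loses 10%, they end at 24.18 × 0.9 = 21.8 and 25.18 × 0.9 = 22.7, so the drug looks better. Yet the share of all patients who lose 7% and end below BMI 18.5 rises from 0.79% to 1.18%. The gap runs from about 0, if background risk is unrelated to BMI, to about 1.4 units at a logit slope of -0.18. At trial size about 4.3% × 167 = 7, 9.1% × 45 = 4 and 9.1% × 167 = 15 patients enter.

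**The case against.** The strongest reply is that the ANOVA would not be read alone. A drug that doubles the number of patients with a 7% loss is what the Fisher test in the preceding sentence looks for. The weight ANCOVA is unrestricted and adjusted, and SAP Appendix 3 also counts a 7% decrease as an abnormal weight, with its own Fisher comparison. The BMI-category test includes the underweight class and, since SAP 5.6 bases safety summaries on the safety population, probably covers everyone. All of this stands and keeps the point small. What remains is that the category test does not state its population, and that the restricted p-value adds nothing reliable to the others.

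The sizes are also open to challenge. They rest on assumed inputs, and under the milder illustration the ANOVA at trial size rejects in only 7.1% of trials (8.0% for 12 mg against placebo), so a misleading significant result would be uncommon. Early termination, recorded in SAP section 3, may thin the data further. That too stands.

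SAP 5.1 says "All analyses will follow the intent-to-treat (ITT) principle unless otherwise specified". It defines this as analysis by assigned arm, which the ANOVA respects. The ANOVA therefore does not contradict that section, but analysis by assigned arm does not undo selection on an outcome.

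A reader might infer that the test has no valid null hypothesis, or that BMI and weight are compared between arms nowhere else. The documents support neither. With no drug effect on weight the subset is selected in the same way in every arm and the level holds (Step 1), and the other analyses in the section are not confined to patients who lost weight.

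**Conclusion.** The point holds in a limited form. The BMI ANOVA conditions on post-randomisation weight loss, the quantity that also drives BMI, and it adjusts for nothing. It is sound if the drug does not affect weight. If the drug does affect weight, which is the case of interest, it can hide, reverse or exaggerate the BMI difference: -0.12, +1.87 or -2.15 against -0.50 to -0.63 in all patients at the middle assumed effect.

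The direction depends on which patients lose weight on drug, and the documents do not say. The numbers show what can happen; they do not predict this trial. Nor do the documents support saying that the test will falsely reassure: that is one of three outcomes. No decision rule hangs on the test, and unrestricted weight comparisons are planned. It is a minor point, worth correcting because the correction costs almost nothing.

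**What to change.** In SAP 5.13.5:

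1. Keep the BMI table for patients with a loss of 7% or more, by arm, with number of patients, baseline BMI and post-baseline BMI. Label it descriptive and delete the ANOVA.
2. State that the BMI-category comparison, including the class below 18.5, uses all safety-population patients with a baseline and a post-baseline weight.
3. Optionally, add the proportion of all those patients who both lose at least 7% and end below BMI 18.5, by Fisher's exact test. This keeps the randomised denominator and addresses the safety question directly.

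The cost is one lost p-value and a little extra tabulation. No new data are needed. The optional item adds up to two tests (each dose against placebo) without multiplicity adjustment. A separate test of the proportion below 18.5 is not needed, because the category comparison largely covers it once its population is stated.

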### **5.13.6. Electrocardiograms**

Electrocardiogram measurements will be analyzed using continuous data (change from baseline) and categorical data (proportion of treatment-emergent abnormalities).

Since ECG is measured in triplicates, the average of triplicates will be used at baseline and each visit. If there are multiple records after averaging ECG triplicates within a visit, the last record of averages will be used.

The analysis will be done for the following ECG measurements: heart rate, PR, QT, QTc, and RR intervals and QRS duration. All analyses of QTc will be carried out using the Fridericia correction (QTcF) method. These summaries will include data from each visit ECG measures are performed. Change from baseline to each post-baseline visit at which ECG measurements are taken and change from baseline to last observation will be assessed using an ANCOVA model. The model for the fixed effects will include terms for the following independent effects: baseline age, baseline ECG score, and treatment. This analysis will be done separately for each ECG parameter.

Incidence of treatment-emergent abnormal ECGs will be assessed by comparisons at (1) anytime and (2) each post-baseline visit between treatment groups with Fisher's exact test. For analyses of treatment-emergent abnormal ECGs, baseline will be considered as all visits before the initiation of drug dose.

Abnormal ECG criteria and criteria for abnormal QTcF prolongation are presented in [Appendix 1](#).

Treatment-emergent high ECG parameters (heart rate, PR interval, QRS duration, QT and QTcF intervals) are the values which are low or normal at all baseline visits and fall into the high

abnormal categories post-baseline. Similarly, treatment-emergent low ECG parameters (Heart Rate, PR interval, QRS duration) are the values which are high or normal at all baseline visits and fall into the low abnormal categories above.

In addition, treatment differences in the proportion of subjects who have normal baselines with a change to abnormal high or abnormal low values at any post-baseline visits will be summarized.

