9.4. Safety

9.4.1. Electrocardiograms

For each patient, triplicate ECGs should be collected according to the Schedule of Activities (Section 2). Electrocardiograms should be recorded according to the study specific recommendations included in the Manual of Operations for the study.

Any clinically significant findings from ECGs that result in a diagnosis and that occur after the patient receives the first dose of the investigational treatment or PET tracers should be reported to Lilly or its designee as an AE via eCRF per Section 9.2.

Electrocardiograms will initially be interpreted by a qualified physician (the investigator or qualified designee) at the site as soon after the time of ECG collection as possible, and ideally while the patient is still present, to determine whether the subject meets entry criteria at the relevant visit(s) and for immediate patient management, should any clinically relevant findings be identified. Patients must meet eligibility criteria with respect to cardiac inclusion/exclusion criteria at the time of the screening. The triplicate ECGs then must be transmitted for central reading.

Note that new findings on ECG after enrollment that do not meet entry criteria do not automatically indicate that subject should be discontinued. In some cases, discontinuation may not be necessary and will depend on clinical significance and implications. The investigator should refer to the Manual of Operations for guidance should a patient's QTcF interval exceed 450 msec (male) or 470 msec (female) or if >30 msec change from baseline while receiving study drug. Unscheduled ECGs may be obtained at the discretion of the investigator.

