9.4.2. Vital Signs

For each patient, vital sign measurements (blood pressure, heart rate, and temperature) must be conducted according to the Schedule of Activities (Section 2) and following the study specific recommendations included in the Manual of Operations for the study. Blood pressure and heart rate will be measured supine and standing.

Any clinically significant findings from vital signs measurements that result in a diagnosis and that occur after the patient receives the first dose of investigational treatment or PET tracers should be reported to Lilly or its designee as an AE via eCRF per Section 9.2.

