## Appendix 1. Potentially Clinically Significant ECGs

---

Parameter	Unit	Low PCS Criteria	High PCS Criteria
QRS Interval	msec	NA	$\geq 120$
PR Interval	msec	NA	$\geq 220$
QTcF	msec	NA	$> 500$
QTc interval: change from baseline		$> 60$ msec at any time after randomization	

---

Abbreviations: NA = not applicable; PCS = potentially clinically significant; QTc = corrected QT interval; QTcF = Fridericia's corrected QT interval.

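### SAP 5.13.6 names eight treatment-emergent ECG categories but Appendix 1 has limits for only three; its QTcF limits leave rises flagged by the protocol uncounted; and SAP 5.13.5 uses a sitting position that the protocol does not name

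*SAP*

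**What the plan says.** **ECG categories.** SAP 5.13.6 states: "Treatment-emergent high ECG parameters (heart rate, PR interval, QRS duration, QT and QTcF intervals) are the values which are low or normal" at every baseline visit and high afterwards. The mirror rule is that "treatment-emergent low ECG parameters (Heart Rate, PR interval, QRS duration) are the values which are high or normal at all baseline visits" and that later "fall into the low abnormal categories above". The section also plans a summary of patients with normal baselines who move to abnormal high or abnormal low. On limits it says: "Abnormal ECG criteria and criteria for abnormal QTcF prolongation are presented in" Appendix 1. Groups are compared by Fisher's exact test at any time and at each post-baseline visit, in line with protocol 10.3.4.

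**Limits.** SAP Appendix 1 has four rows: QRS (high from 120 msec), PR (high from 220 msec), QTcF (high above 500 msec) and "QTc interval: change from baseline" (above 60 msec). The low column reads NA for QRS, PR and QTcF.

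**Protocol on QTcF.** Section 9.4.1 sends the investigator to the Manual of Operations should a patient's "QTcF interval exceed 450 msec (male) or 470 msec (female"), or should it change by more than 30 msec from baseline on study drug. Exclusion criterion 23 uses the same 450 and 470 msec at screening.

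**Position.** SAP 5.13.5 lists blood pressure and pulse "collected in sitting position", next to orthostatic differences between supine and standing readings. Protocol 9.4.2 says: "Blood pressure and heart rate will be measured supine and standing".

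**The concern.** A category without a limit cannot be programmed. Someone would have to choose the missing ECG limits after the SAP was final, possibly with the data in view, or drop the tables without saying so.

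The QTcF limits matter because QT is a declared concern in this trial. Congenital QT prolongation is excluded, QT-prolonging drugs are prohibited, tracer scans are restricted on QT and Torsades grounds (protocol 7.1.2), and the SAP lists a Torsades/QT search among its adverse events of special interest. An outlier table is where a reader looks for individual patients with large rises, and a mean does not show them.

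The sitting wording leaves it unclear which readings feed the main blood pressure and pulse summaries.

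**Working it through.** No sample size or power figure is involved. The check sets the passages side by side, with simple arithmetic on the QTcF limits.

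**1. Eight categories against Appendix 1**

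| Category in SAP 5.13.6 | Limit in Appendix 1 |
|---|---|
| High PR | 220 msec or more |
| High QRS | 120 msec or more |
| High QTcF | above 500 msec (separate row: change above 60 msec) |
| High heart rate | no row |
| High QT | no row |
| Low heart rate | no row |
| Low PR | NA |
| Low QRS | NA |

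There are 5 high + 3 low = 8 categories. Limits exist for 3 of 5 high and 0 of 3 low, so 8 − 3 = 5 have none. The three with limits can be run, since low or normal at baseline then simply means not high. The text places the low categories earlier in the section, but none are set out there. The normal-to-abnormal summary fails for the same five.

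The pulse limits in SAP Appendix 3 do not fill the heart-rate gap. They require an observed value (120 or more, or 50 or less) and also a change of at least 15 bpm from baseline. SAP 5.13.6 must first classify the baseline visits themselves, and a baseline value has no change from baseline.

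**2. QTcF values that are flagged but not counted**

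Let b be baseline QTcF in msec.
- The protocol flags a value above the smaller of 450 (men) or 470 (women) and b + 30.
- Appendix 1 counts a value above the smaller of 500 and b + 60.

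Illustrative baselines (assumed):

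| Patient | Flagged above | Counted above | Uncounted width |
|---|---|---|---|
| Man, b = 400 | min(450, 430) = 430 | min(500, 460) = 460 | 30 |
| Man, b = 440 | min(450, 470) = 450 | min(500, 500) = 500 | 50 |
| Man, b = 450 | min(450, 480) = 450 | min(500, 510) = 500 | 50 |
| Woman, b = 470 | min(470, 500) = 470 | min(500, 530) = 500 | 30 |

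A man going from 440 to 495 changes by 495 − 440 = 55. He is above 450 and above +30, but not above 500 and not above +60. A man going from 400 to 465 changes by 65 and is both flagged and counted. The tables therefore miss some flagged rises, not all of them.

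**3. Position**

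The protocol names supine and standing; SAP 5.13.5 names sitting for the summaries. The orthostatic measures use supine and standing, and Appendix 3 accepts supine or sitting for its blood pressure and pulse limits, so both can run on the protocol's readings. Only the non-orthostatic summaries and change-from-baseline analyses of blood pressure and pulse are affected.

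**The case against.** The best case for the plan is on QTcF. The 450, 470 and +30 values are entry and site-guidance points. Protocol 9.4.1 adds that new ECG findings do not by themselves require discontinuation. Appendix 1 is a list of potentially clinically significant values and may set a higher bar. QT is also covered elsewhere: SAP 5.13.6 analyses mean change in heart rate, PR, QT, QTcF, RR and QRS by ANCOVA at each ECG visit and at last observation, and SAP 5.13.3 with its Table LLCF.SAP.3 compares adverse-event groups that include the Torsades/QT search. ECGs are also read centrally.

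Most of this stands, and it rules out three stronger readings that a reader might infer.

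- *The SAP contradicts the protocol on QTcF.* It does not. The two sets of values serve different purposes, and the protocol never declares its own as analysis limits.
- *The plan would miss a QT effect, or its outlier tables would be empty.* The documents do not support this. The mean-change analysis remains, some flagged rises are counted, and no drug effect or SD for QTcF is given from which to predict event counts.
- *Sitting readings are never taken, so the blood pressure analysis has no data.* This cannot be shown. Protocol 9.4.2 also relies on a Manual of Operations that is not among the documents.

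The objection does not reach the five categories without limits. Nor does mean-change coverage, or a search that depends on an event being reported, replace a count of individual QTcF outliers.

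**Conclusion.** The point holds in three parts of unequal weight.

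- **Internal mismatch (firm).** Five of the eight treatment-emergent ECG categories have no limit and cannot be counted as written. This rests only on the SAP's own text.
- **QTcF coverage gap (real but limited).** At the baselines worked through, a band of 30 to 50 msec is flagged by the protocol and uncounted by the SAP. The baselines are assumed. How many patients would fall in the band cannot be estimated from the documents.
- **Position (a wording inconsistency).** The SAP summarises a position that the protocol does not name.

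The effect is confined to safety tables: the categorical ECG tables and the non-orthostatic blood pressure and pulse summaries. Efficacy is untouched. The changes are worth making because safety is a stated objective, QT is a declared concern, and the ECG changes need no new data.

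**What to change.** 1. **Add QTcF reporting rows.** Beside above 500 and change above 60 msec, tabulate the protocol's own values: above 450 msec (men), above 470 msec (women), and increase above 30 msec. Label them as reporting categories only. They change no patient's management and imply no view on which clinical limit is right.
2. **Reconcile SAP 5.13.6 with Appendix 1 before database lock.** Either add limits that can classify both baseline and post-baseline values, or delete the counts that have none. The documents do not show which passage is wrong, so the sponsor must decide and record the reason. Do not transplant the Appendix 3 pulse limits.
3. **Reconcile the position in SAP 5.13.5** with the supine and standing readings in protocol 9.4.2, stating which reading the summaries use.

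The cost is a short SAP edit and a few more table rows. The triplicate ECGs and the supine and standing readings are already in the protocol.
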